4.7. Statistical methods

For futility testing in Stage 1, a responder rate definition will be used. Patients randomized to receive pamrevlumab are considered responders if the total number of days on ventilation is \leq 15 days after the first dose of pamrevlumab. In addition, chest HRCT scans obtained at enrollment and day 14 \pm 2 will used as supportive analyses in the assessment of futility.

Analysis of continuous endpoints will be conducted using analysis of covariance (ANCOVA) model with baseline value as a covariate and relevant baseline prognostic factors as other covariates.

Analysis of categorical endpoints will be conducted using either Fishers Exact test or Cochran-Mantel-Haenszel test comparing the categories between the two treatment arms.

Analysis of the time to mechanical ventilation, time to all-cause mortality, and time to hospital discharge, respectively, will be undertaken by plotting Kaplan-Meier curves. Hazard ratios will be estimated using the Cox proportional hazards model and these will be presented together with 95% two-sided confidence intervals. Other statistical methods will be applied, as appropriate.

5. Subject withdrawal criteria

Subjects may withdraw from the study at any time, for any reason. Reasons for discontinuing study drug treatment, as well as reasons for withdrawing from study, will be captured on CRF.

Reasons for withdrawing the subject from the study may include the following:

- 5.1. Any safety concern in the Investigator's opinion, that precludes further study participation
- 5.2. Pregnancy
- 5.3. Withdrawal of Consent

6. Pamrevlumab: storage, preparation and use

Pamrevlumab is a fully human IgG1 kappa monoclonal antibody that binds to CTGF and is formulated as solution for administration by IV infusion.

Pamrevlumab is supplied in single-use glass vials containing sterile, preservative-free solution 10 mg/ml pamrevlumab. The solution is composed of 10 mg/mL pamrevlumab, 1.60 mg/mL L-histidine, 3.08 mg/mL L-histidine HCl, 8.01 mg/mL sodium chloride, and 0.05 mg/mL polysorbate 20, resulting in a solution with a tonicity of approximately 290 mmol/kg and a pH of 6.0.

Vials of pamrevlumab must be stored refrigerated (2°C to 8°C), in a temperature- controlled and monitored environment, protected from light, and in a securely locked area to which access is limited to appropriate study personnel. Documentation of the storage conditions must be maintained.

Pamrevlumab is infused undiluted after pooling the contents of the calculated number of vials in an empty infusion bag (total volume of fluid must not exceed 410 mL)

Pamrevlumab must be stored refrigerated (2°C to 8°C) and administered within 24 hours of preparation. Pamrevlumab or placebo infusion solutions are administered by IV infusion, using an infusion set with a 0.2 μ m in-line filter.

Dosing will be based on the weight. The total dose of study drug is not to exceed 4.1g. Study Drug will be administered within 24 hours of preparation if stored 2°C-8°C or within 6 hours if stored at room temperature. Study Drug will be administered by IV infusion, using an infusion set with a sterile, nonpyrogenic, low-protein-binding in-line filter (0.2-micron pore size).

Before and after each infusion vitals and AE assessments will be completed. The first 3 study drug infusions will last approximately 2 hours in duration. If the first 3 infusions are well tolerated, all other infusions will be shortened to 60 minutes in duration. Vital signs and assessment of AEs, including any symptoms of hypersensitivity and anaphylactic reactions, will be observed as follows: 2 hours after the first 3 infusions, followed by 1 hour, if the first 3 infusions were well tolerated.

If a patient experiences a hypersensitivity or anaphylactic reaction, the infusion should be immediately stopped; such a patient should be discontinued from further treatment, and followed for safety, up to 4 weeks after the last infusion.

All study drug is provided by FibroGen. All used and unused vials should be accounted for and drug accountability documentation will be maintained. Used and unused vials can be discarded. Records of destruction will be maintained.

7. Safety

All AEs observed or reported spontaneously during the course of the study will be recorded. Reports of hypersensitivity and anaphylactic reactions will be carefully monitored, including by the FibroGen Drug Safety department, as well as by an independent Data and Safety Monitoring Board (DSMB), as soon as it is assembled. An adverse event is defined as any untoward medical occurrence in a clinical trial subject. The event does not necessarily have a causal relationship with study treatment. The investigator is responsible for ensuring that any adverse events observed by the Investigator or reported by the subject as defined in the study protocol are recorded in the subject's medical record.

The following attributes must be assigned to each AE:

- 7.1. Description (Investigator's verbatim term describing the event)
- 7.2. Dates of onset and resolution
- 7.3. Severity
- 7.4. Relationship to study drug
- 7.5. Outcome
- 7.6. Action taken regarding study drug
- 7.7. Other treatment required
- 7.8. Determination of "seriousness"

To date over 600 patients are exposed to pamrevlumab, few with IPF up to five years, and others for more than 4 years with non-ambulatory Duchenne Muscular Dystrophy. As of to-date, no treatment-emergent serious adverse events of allergic or anaphylactic reactions were observed. However, the study drug will be stopped and study terminated if signs of serious allergic reactions are observed.

Blood-samples to determine immunogenicity: human-anti-human antibodies (HAHAs) will be collected prior to first dose, at regular intervals: days 7 and 14 during treatment, as well as at the last visit, 12 weeks after the end of treatment, as part of safety analyses.

8. Data collection, handling, and verification

Source documents are original documents, data, and records necessary for the reconstruction and evaluation of the clinical study. All required data will be entered onto source documents by authorized site personnel and all data including lab reports will be provided to FibroGen to be entered into a validated, clinical database compliant with 21 CFR Part 11 regulations.

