3. STUDY ENDPOINTS

3.1. Primary endpoint

Proportion of patients not on ventilatory support \leq 15 days.

and qualitative changes by an independent imaging group.

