3.2. Futility testing

Futility testing will be performed when 23 pamrevlumab patients completed 14 days of treatment. For futility testing of Stage 1 of the study, a responder rate definition will be evaluated. Patients randomized to receive pamrevlumab are considered responders if the total number of days on mechanical ventilation is ≤15 days after first dose of pamrevlumab and the patient is alive. In addition, chest high-resolution CT (HRCT) scans obtained at baseline and day 14 will used as supportive analyses in the assessment of futility. Such analyses will be based on both quantitative

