4.3. Diagnosis and main criteria for inclusion

Eligible patients are those with documented COVID-19, age \geq 18 to \leq 80 years with interstitial pneumonia (findings of consolidation or ground glass opacities as assessed by chest HRCT) and respiratory distress, defined as PaO₂/FiO₂ ratio of \geq 100 \leq 300 mmHg, requiring supplemental oxygen and hospitalization.

Exclusion criteria for the study are the following:

- Invasive mechanical ventilation at screening;
- Pregnancy;
- Incapacity to express a valid informed consent;
- Known hypersensitivity to monoclonal antibodies used as experimental drugs for any clinical indication.

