4.6. Determination of sample size

This study's sample size is based on Simon's two-stage design (Simon, 1989) on the pamrevlumab arm. For futility testing of Stage 1 of the study, a responder rate definition will be evaluated. Patients randomized to receive pamrevlumab are considered responders if the total number of days on ventilation is \leq 15 days after first dose of pamrevlumab and the patient is alive.

Key assumptions for sample size calculation include the following: (1) type I error rate, α (one-sided): 0.05; (2) power: 90%; (3) response probability of standard of care: 40%; (4) response probability of standard of care + pamrevlumab: 65%.

The null hypothesis that the true response rate is 40% will be tested against a one-sided alternative. In Stage 1, 23 patients will be accrued in pamrevlumab arm. If there are 9 or fewer responses in

these 23 patients, the study may be stopped. Otherwise, 11 additional patients will be accrued for a total of 34 in pamrevlumab treatment group. The null hypothesis will be rejected if 18 or more responses are observed in 34 patients on the pamrevlumab arm. This design yields a type I error rate of 0.05 and power of 90% when the true response rate is 65%.

The study will enroll approximately 50 patients in Stage 1 who will be randomized in 1:1 fashion (pamrevlumab vs. standard of care).

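### Section 4.7 drops the survival condition from the Stage 1 futility responder, so a patient who dies by Day 15 counts as a response

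*Protocol*

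**What the plan says.** Three sections describe the responder for the same Stage 1 futility test in the pamrevlumab arm.

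- Section 3.2 (Futility testing): "the total number of days on mechanical ventilation is ≤15 days after first dose of pamrevlumab and the patient is alive".
- Section 4.6 (Determination of sample size): "the total number of days on ventilation is \leq 15 days after first dose of pamrevlumab and the patient is alive". The decision rule is also here: the study may stop if there are 9 or fewer responses among 23 pamrevlumab patients. The assumed response rates are 40% (null) and 65%.
- Section 4.7 (Statistical methods): "considered responders if the total number of days on ventilation is \leq 15 days after the first dose of pamrevlumab". The sentence ends there, with no mention of survival.

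Section 3.2 also sets the timing: "Futility testing will be performed when 23 pamrevlumab patients completed 14 days of treatment". None of the three sections gives a date for survival status or a closing day for the ventilation-day count.

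The primary endpoint in 3.1 reads "Proportion of patients not on ventilatory support \leq 15 days" and does not mention death.

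**The concern.** Death is the worst outcome in this trial, and the same death is scored in opposite directions depending on which section is applied. Under 4.7 a patient who dies early has had little time to be ventilated, and so meets the criterion because of the death. The more early deaths in the pamrevlumab arm, the higher its response count.

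The count feeds a decision to stop or continue. The 40% and 65% in 4.6 directly follow a definition that includes survival, so they do not describe a variable that scores early deaths as responses. The trial is open-label, and two conflicting definitions leave room to choose between them after outcomes are known. An analysis plan could not settle this without departing from one section of the protocol.

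**Working it through.** **1. One patient under each section.** Day 1 is the day of randomization and first dose (section 4.1), and patients with "Invasive mechanical ventilation at screening" are excluded. Take a patient who dies on Day 5. Ventilation days after first dose number between 0 and 5, which is no more than 15. Under 4.7 this is a responder; under 3.2 and 4.6 it is a non-responder. The same holds for any death up to and including Day 15, because at most 15 calendar days are available.

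**2. The plan's own figures.** An exact search for a two-stage Simon design (null 0.40, alternative 0.65, one-sided 0.05, power at least 0.90) gives as its minimax solution 23 patients in Stage 1, stop at 9 or fewer, 34 in total. The sample sizes and the Stage 1 boundary in 4.6 therefore reproduce. That solution rejects at 19 or more of 34 (type I error 0.044, power 0.900). The printed cut-off of 18 gives 0.086 and 0.947. The final cut-off is a separate matter and does not enter below.

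**3. Effect on the Stage 1 rule.** Inputs:

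- n = 23, continue at 10 or more responses (4.6).
- True rate of being alive with 15 or fewer ventilation days: 0.40, the null in 4.6.
- d = share of patients who die with 15 or fewer ventilation days. The protocol gives no figure, so 0.05, 0.10 and 0.20 are assumed.
- The 23 are taken as patients accrued, as 4.6 has it, so early deaths stay in the denominator.

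Under 3.2 and 4.6 the scored rate is p = 0.40. Under 4.7 it is p = 0.40 + d. The chance of passing Stage 1 is

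P(X ≥ 10) = 1 − Σ C(23, x) pˣ (1 − p)²³⁻ˣ, summed over x = 0 to 9.

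| d (assumed) | Expected such deaths in 23 | p scored under 4.7 | P(9 or fewer) | P(pass Stage 1) |
|---|---|---|---|---|
| 0 | 0 | 0.40 | 0.556 | 0.44 |
| 0.05 | 0.05 × 23 = 1.15 | 0.45 | 0.364 | 0.64 |
| 0.10 | 0.10 × 23 = 2.3 | 0.50 | 0.202 | 0.80 |
| 0.20 | 0.20 × 23 = 4.6 | 0.60 | 0.035 | 0.97 |

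The first row is also the answer under 3.2 and 4.6 whatever the value of d, since those sections score the deaths as non-responses.

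**4. Effect of the timing in 3.2.** If patients were scored on about 14 days of follow-up, the largest possible ventilation count would be 14, which is below the limit of 15. Under 4.7 all 23 would be responders and the rule of 9 or fewer could never trigger. Under 3.2 and 4.6 survival would be the only component separating responders from non-responders.

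**The case against.** The strongest reply is that 4.7 is a shortened restatement. It contains no cut-off; the whole rule sits in 4.6 beside the definition with survival, and 3.2, the section on futility, agrees. The stop is permissive, HRCT is supportive, safety is analysed at the same look, a data review committee is involved, and mortality is a separate endpoint in 3.3.9 and 3.3.11. Excess deaths would therefore be seen. All of this is fair and lowers the practical risk. It does not remove the conflict: 4.7 is the statistical methods section, and it defines a count that informs stopping in a way that rewards early death.

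A reader might infer three stronger points, which the protocol does not support.

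- *That 3.1 contradicts 3.2 and 4.6.* Those sections attach survival to the Stage 1 responder and do not expressly impose it on the primary endpoint. The wording of 3.1 is ambiguous, and a death counts as a success there only on one literal reading. This is a separate ambiguity.
- *That the false-positive rate of the final 34-patient test is inflated.* The definition in 4.7 is introduced for Stage 1 futility only, and the final rule is in 4.6, where survival is required. Carrying the 4.7 scoring to 34 patients needs an added assumption.
- *That survival at Day 28, already used in 3.3.9 to 3.3.11, is a wording-only remedy.* The look comes when 23 patients have completed 14 days, and the schedule of events provides the Day 28 contact only for patients whose treatment ends on Day 14.

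**Conclusion.** The point holds for the Stage 1 futility responder. Section 4.7 conflicts with 3.2 and 4.6, and followed as written it scores every death by Day 15 as a response. At a true alive-responder rate of 40%, the chance of passing Stage 1 rises from 0.44 to 0.64, 0.80 or 0.97. These figures rest on assumed shares of 5, 10 and 20 points of patients who die with 15 or fewer ventilation days; the direction of the error does not depend on them. If scoring used only about 14 days of follow-up, the 4.7 definition would make futility impossible to declare. The definition needs correcting before the Stage 1 look. Section 3.1 needs clarifying, but as a lesser and separate matter.

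**What to change.** 1. Add the survival condition to 4.7 so that it matches 3.2 and 4.6, and state that any death by the assessment day is a non-response whatever the number of ventilation days.
2. In all three sections, state one assessment day for both survival status and the ventilation-day count. It must be compatible with the Stage 1 look, or the look must move to that day. A limit of 15 days separates patients on ventilation only if more than 15 days are observed.
3. Use one term for ventilation; 3.2 says mechanical ventilation, while 4.6 and 4.7 say ventilation only.
4. Separately, in 3.1, state that a patient who dies within the primary endpoint window is not a success.

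Cost: items 1, 3 and 4 are wording. The observed response rate may be lower than under the 4.7 wording. Item 2 may delay the look slightly if the chosen day falls after Day 14. It would also require ventilation status to be recorded up to that day, because the oxygen-supplementation row of the schedule of events, which covers mechanical ventilation, ends at Day 14.

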3.3. Secondary endpoints

3.3.1. PaO_2/FiO_2 ratio as categorical variable: mild 200 mmHg < $PaO_2/FiO_2 \le 300$ mmHg; moderate 100 mmHg < $PaO_2/FiO_2 \le 200$ mmHg; severe $PaO_2/FiO_2 \le 100$ mmHg.

- 3.3.2. For patients already on mechanical ventilator at time of randomization, the number of days on ventilator after randomization.
- 3.3.3. For patients not on mechanical ventilator at time of randomization, the number of days not requiring invasive mechanical ventilation (i.e., ventilator-free days).
- 3.3.4. PaO_2/FiO_2 ratio as continuous variable.
- 3.3.5. Resting SpO₂ adjusted by FiO₂.
- 3.3.6. Change in oxygen supplementation requirements.
- 3.3.7. Quantitative and qualitative assessment of pulmonary lesions by chest HRCT scans at baseline and at day 14 and week 12.
- 3.3.8. Time to hospital discharge.
- 3.3.9. Time to all-cause mortality up to 28 days.
- 3.3.10. Proportion of patients discharged from ICU and alive within 28 days.
- 3.3.11. Proportion of patients alive within 28 days.

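### Section 4.7 drops the survival condition from the Stage 1 responder definition, the primary endpoint is silent on death, and the ventilation term is never fixed

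*Protocol*

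**What the plan says.** The protocol describes response in four places.

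- **3.1, primary endpoint:** "Proportion of patients not on ventilatory support \leq 15 days". Death is not mentioned.
- **3.2, futility testing:** the patient responds if the "total number of days on mechanical ventilation is ≤15 days after first dose of pamrevlumab and the patient is alive".
- **4.6, sample size:** the patient responds if the "total number of days on ventilation is \leq 15 days after first dose of pamrevlumab and the patient is alive".
- **4.7, statistical methods:** patients are "responders if the total number of days on ventilation is \leq 15 days after the first dose of pamrevlumab". The sentence ends there, with no survival condition.

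Sections 3.2, 4.6 and 4.7 all introduce their definition for Stage 1 futility testing in the pamrevlumab arm. Section 4.6 then uses responses, without a second definition, for the final rule of 18 or more in 34.

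The exposure changes name as well: *ventilatory support* in 3.1, *mechanical ventilation* in 3.2 and plain *ventilation* in 4.6 and 4.7. Secondary endpoint 3.3.3 uses a fourth term, "the number of days not requiring invasive mechanical ventilation (i.e., ventilator-free days". None is defined. Section 4.3 excludes only invasive mechanical ventilation at screening.

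Section 3.2 places the Stage 1 look at the point when 23 pamrevlumab patients have completed 14 days of treatment.

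**The concern.** Two definitions of the same responder classify the same patient differently, and nothing says which prevails. Section 4.7 is where an analyst would look first. Because the trial is open label, the choice could be made after outcomes are known.

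The design tests the pamrevlumab arm against a fixed 40%, so no concurrent control offsets deaths that are counted as responses. The 40% and 65% rates stand in 4.6 beside the definition that requires survival. If survival is dropped, those rates no longer describe the quantity being counted.

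The ventilation wording is a separate ambiguity. Patients on non-invasive support can enter the trial, so whether that support counts towards the 15 days affects who responds.

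**Working it through.** **Step 1. Classify the same patients under each text.**

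| Patient | 3.2 and 4.6 | 4.7 | 3.1 |
|---|---|---|---|
| Dies on Day 3, never ventilated (0 days) | non-responder | responder | not stated |
| Ventilated from Day 1, dies by Day 15 (at most 15 days) | non-responder | responder | not stated |
| Alive, 15 or fewer days on ventilation | responder | responder | depends on the term |

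The Stage 1 timing sharpens this. A patient with only 14 days of follow-up cannot have accumulated more than 15 ventilation days. For such a patient, survival is the only condition that can produce a non-response, and 4.7 omits it.

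**Step 2. Reproduce the plan's own figures.** Inputs from 4.6: 23 patients in Stage 1, stop at 9 or fewer, 11 more for a total of 34, null rate 40%, alternative 65%, stated type I error 0.05 and power 90%. With final boundary R and response rate p:

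P(stop) = P(Bin(23, p) ≤ 9)

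P(success) = Σ over x = 10 to 23 of P(Bin(23, p) = x) × P(Bin(11, p) ≥ R − x)

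| R | P(success) at 40% | P(success) at 65% |
|---|---|---|
| 18 or more (as written) | 0.086 | 0.947 |
| 19 or more | 0.044 | 0.900 |

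The stated 0.05 and 90% do not reproduce at 18 but fit 19. That is a separate boundary error. It matters here only because the baseline at 18 is 0.086, not 0.05. Both boundaries are carried below.

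**Step 3. Add deaths counted as responses.** Let d be the share of patients who die but count as responders. The protocol gives no such figure, so d is an assumption. The drug is inert: the true rate of responding and being alive is 40%. The Stage 1 rule is treated as followed, although 4.6 says only that the study may be stopped.

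*Case A: 4.7 governs Stage 1 only, and the final count follows 4.6.* Stage 1 is passed if alive responders A plus counted deaths K reach 10 of 23. Success then needs A plus the alive responders among the next 11 to reach R. (A, K) is trinomial with probabilities 0.40 and d. P(stop) = P(Bin(23, 0.40 + d) ≤ 9).

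*Case B: deaths also count in the final 34.* Put p = 0.40 + d into both formulas of Step 2.

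| d | P(stop), A and B | A: success, R = 18 | A: success, R = 19 | B: success, R = 18 | B: success, R = 19 |
|---|---|---|---|---|---|
| 0 | 0.556 | 0.086 | 0.044 | 0.086 | 0.044 |
| 5 points | 0.364 | 0.087 | 0.044 | 0.221 | 0.135 |
| 10 points | 0.202 | 0.087 | 0.044 | 0.429 | 0.303 |
| 15 points | 0.094 | 0.087 | 0.044 | 0.658 | 0.529 |

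Case A cannot exceed the single-stage value P(Bin(34, 0.40) ≥ R), which is 0.0872 at 18 and 0.0444 at 19. Removing the Stage 1 stop altogether would do no more harm than that to the false-positive rate.

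**The case against.** The strongest objection concerns reach. Section 4.7 limits its definition to Stage 1 futility testing, and the final rejection rule appears only in 4.6, whose own definition requires survival. On that reading the false-positive rate stays at its baseline. This stands. A reader might infer that the missing condition by itself raises the false-positive rate to 0.22 or more. The documents do not support that: it requires deaths to count in the final 34 as well, in place of the 4.6 definition.

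A reader might also set 0.22 against the stated 0.05 and blame the whole gap on deaths. At 18 or more, 0.086 is already present with no deaths miscounted.

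Third, 3.1 might be read as plainly scoring death as success. It is one loosely worded sentence that does not mention death. Success for an unventilated death is its literal reading, but the certainty attaches only to 4.7.

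Fourth, it is tempting to take *invasive* as the intended meaning because 3.3.3 and the exclusion criteria use it. Nothing ties that term to the primary endpoint or to the 40% and 65% rates.

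Finally, mortality is assessed separately (3.3.9 and 3.3.11), Stage 1 includes a safety analysis, and a data review committee and a DSMB are foreseen. A claim that the plan would let a life-shortening drug pass unnoticed would therefore go too far. These safeguards limit the consequence but do not settle which definition of response applies.

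**Conclusion.** Wrong as written. Section 4.7 contradicts 3.2 and 4.6 on whether a dead patient can be a responder, and 3.1 leaves the scoring of death open. This is not detail left to a SAP, because the protocol itself gives both definitions.

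The effect that follows from the narrow reading of 4.7 is on futility stopping: for an inert drug the chance of stopping falls from 0.556 to 0.364, 0.202 or 0.094 if 5, 10 or 15 points of patients die and are counted. The larger effect, success probabilities of 0.22, 0.43 or 0.66 at 18 or more (0.13, 0.30 or 0.53 at 19 or more), is conditional on carrying deaths into the final test. All of these rest on the assumed death shares and on a true alive-response rate of 40%.

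The undefined ventilation terms are a second, independent defect. Its size cannot be computed from the protocol.

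**What to change.** Use one definition in 3.1, 3.2, 4.6 and 4.7, for both arms, counted from Day 1. Section 4.1 makes Day 1 the day of randomisation and, in the active arm, of the first dose, so the count also works for patients who receive no pamrevlumab. A responder is alive at a stated assessment day and has had 15 or fewer days on ventilation; death before that day is non-response.

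Use one defined ventilation term throughout, the one on which the 40% and 65% rates were based, and state whether non-invasive support counts.

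Set the assessment day late enough that more than 15 ventilation days can be observed, and reconcile it with the Stage 1 look after 14 days of treatment.

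The cost is protocol wording and possibly a slightly later Stage 1 look. The planned numbers (23 in Stage 1, 34 in the pamrevlumab arm, about 68 in all) do not change.

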4. STUDY DESIGN AND METHODS

4.1. Study design

This is a randomized, open-label, parallel-arm study to investigate the efficacy and safety of pamrevlumab in patients with documented SARS-CoV-2 infection. The study consists of screening, a treatment period, and a follow-up period.

The study will enroll patients who have been hospitalized and who are not currently on invasive mechanical ventilation. The treatment period is open ended, and patients will be randomized to treatment with pamrevlumab or standard of care in a 1:1 ratio according to a pre-generated randomization list. Pamrevlumab dosing, 30 mg/kg IV, will be administered at day 1, day 7 and day 14. Day 1 is defined as the day of randomization which must also include administration of the first dose of pamrevlumab for patients in the active treatment arm.

Based on Investigator's decision, treatment may be continued every 3 weeks after day 14, up to 11 weeks.

Since the treatment scheme of pamrevlumab for this study is more intense as compared to previous studies conducted in IPF patients, as a further safety measure the first 3 patients randomized to receive the experimental drug will be treated one at a time, leaving a 1-week observation period between them.

A follow-up by visit or phone call will be performed 8 and 12 weeks after the end of the last dose of treatment. The treatment period for an individual patient will not exceed 11 weeks. The end of the study is defined as last patient last follow-up visit/phone call.

The study design has a total sample size of approximately 68 patients and consists of two stages. At the end of Stage 1 (Stage 1 requires 23 patients on pamrevlumab treatment arm), analyses of efficacy and safety will take place with a potential to stop the study for futility or for efficacy. A data

review committee composed of experts in respiratory medicine and intensive care will be involved in study oversight and interpretation of the study results. In patients showing worsening of clinical condition, independently of the treatment arm, the Investigator is free to introduce any therapy considered necessary.

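### Section 4.7 names only baseline-adjusted ANCOVA for daily oxygenation readings that stop at ICU/CCU discharge; a repeated-measures model would handle them better

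*Protocol*

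**What the plan says.** Section 4.7 assigns one method to continuous endpoints: "Analysis of continuous endpoints will be conducted using analysis of covariance (ANCOVA) model with baseline value as a covariate", with prognostic factors at baseline as further covariates. It names no repeated-measures term, analysis day or summary measure. The section closes with a general allowance: "Other statistical methods will be applied, as appropriate".

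Section 3.3 lists "PaO_2/FiO_2 ratio as continuous variable" (3.3.4) and "Resting SpO₂ adjusted by FiO₂" (3.3.5) without a day or window. Other items in the list do carry times. Item 3.3.7 reads "Quantitative and qualitative assessment of pulmonary lesions by chest HRCT scans at baseline and at day 14 and week 12", and 3.3.9 to 3.3.11 refer to 28 days.

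The schedule of events (section 9) marks blood gases, PaO2/FiO2 and SpO2 on each day from Day 1 to Day 14, with SpO2 three times a day. Footnote 3 limits these readings to the time before the patient leaves the ICU or CCU.

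**The concern.** ANCOVA with a baseline covariate takes one outcome value per patient. The data here are a series of up to 13 post-baseline days (Days 2 to 14), and that series is cut short in patients who do well enough to leave intensive care.

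On a late day, those still measured are mainly the patients who have not recovered. If the drug works, more treated than control patients will have left, so the comparison sets the slower treated patients against a less selected control group. The readings that discharged patients gave earlier do not enter the analysis.

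Improved gas exchange is the first mechanism offered in the study rationale (section 1.6), so these are the endpoints on which an understated effect would be most misleading. With about 68 patients randomised 1:1, or about 34 per arm, there is little precision to spare.

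**Working it through.** **Inputs from the protocol.** About 34 per arm (sections 4.1 and 4.2, 68/2). Daily readings on Days 1 to 14, ending at ICU/CCU discharge (section 9, footnote 3). ANCOVA adjusted for baseline (section 4.7). The protocol states no SD, effect size, correlation or power for these endpoints, so there is no figure of its own to reproduce.

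**Assumed inputs.** Baseline PaO2/FiO2 mean 190 mmHg, SD 55. Mean rise of 6 mmHg per day in control and 9 on drug. Within-patient correlation 0.4 + 0.6 × 0.8^lag. Readings stop after two days above 300 mmHg. Two-sided 5% tests. No deaths.

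**True effect.** The arms diverge by 9 − 6 = 3 mmHg per day. At Day 14, 13 days after baseline, the difference is 3 × 13 = 39 mmHg. Averaged over Days 8 to 14 it is 3 × (7 + … + 13)/7 = 3 × 10 = 30 mmHg.

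**Step 1: Day 14 ANCOVA if nobody is discharged.**
- Correlation of baseline with Day 14: 0.4 + 0.6 × 0.8^13 = 0.433.
- Residual SD after baseline adjustment: 55 × √(1 − 0.433²) = 49.6 mmHg.
- Standard error of the arm difference: 49.6 × √(2/34) = 12.0 mmHg.
- Power: Φ(39/12.0 − 1.96) ≈ 90%.

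With complete data, therefore, Day 14 ANCOVA performs well under these assumptions.

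**Step 2: the same trial with readings ending at discharge (simulation).** About 64% of all patients, and about 54% of the drug arm, still have a Day 14 value. With equal arms, that leaves about 2 × 64 − 54 = 74% of controls.

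| Analysis | Estimate at Day 14 (true 39) | Power |
|---|---|---|
| ANCOVA, Day 14, available values | about 28 mmHg | 53% |
| ANCOVA, mean of each patient's available days | different estimand | 60% |
| Longitudinal model, all readings, Day 14 contrast | about 40 mmHg | 79% |

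Repeat runs gave 27 mmHg with 49 to 52% power for Day 14 ANCOVA, and 38.6 to 38.9 mmHg with 77 to 80% power for the longitudinal model. The shortfall is (39 − 28)/39 = 28%, or 31% at 27 mmHg.

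**Step 3: why a summary measure does not repair it.** An ANCOVA on the mean of available days keeps every patient. However, an early-discharged patient's mean covers only the first days, when the arms have diverged least, so means over different spans are being compared. Its power (60%) is closer to that of the single-day analysis than to that of the longitudinal model.

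**Step 4: does a window average help by itself?** Across the correlation structures tried, the baseline-adjusted variance of the Days 8 to 14 mean is 0.46 to 0.72 of that of Day 14 alone. An effect with 60% power at Day 14 has noncentrality 1.96 + 0.25 = 2.21.
- Constant effect over those days: 2.21/√0.72 = 2.61 and 2.21/√0.46 = 3.26, giving 74% to 90% power.
- Effect growing as assumed above (30 against 39): multiply by 30/39, giving 2.01 and 2.51, or 52% to 71% power.

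The gain from averaging depends on the shape of the effect. It is not part of the case for changing the model.

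**The case against.** The strongest reply is that section 4.7 is less restrictive than it may look. A reader might infer that it fixes one value per patient and discards the other 12 days. It does not say so: ANCOVA can be fitted to a mean or an area under the curve, and the closing sentence admits other methods. That stands, and the point does not depend on the stronger reading. What remains is that the only named method suits discharge-truncated series less well, whether applied to a late day or to the available-day mean.

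A reader might also infer that the analysis day can be chosen from open-label results. Under assumed correlations, testing all 13 days at 5% and keeping the best would give 24 to 44% false positives. That would require that no day is named before the data are seen. The analysis day is ordinary content for a statistical analysis plan, which may exist but is not shown, so the documents do not support the inference.

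The illustration favours the longitudinal model in some respects. Discharge depends only on observed values, so missingness is at random by construction. The covariance is taken as known, and death and intubation are absent. This is a fair limit on the size. The direction could also differ if deaths rather than recoveries dominate the missing values. Finally, eligibility (section 4.3) does not require ICU admission, so it is unclear how footnote 3 works for ward patients and how many series would be cut short.

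**Conclusion.** The point holds as a matter of method. For 3.3.4 and 3.3.5, baseline-adjusted ANCOVA is a poorer choice than a repeated-measures model, because readings are daily and stop at ICU/CCU discharge. If discharge follows observed oxygenation, a late-day ANCOVA on available values understates a real effect. In the illustration it does so by about 30%, with 53% power against 79%.

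The advantage comes from how discharge is handled. With complete data, Day 14 ANCOVA reaches about 90% power in the same setting. All sizes rest on the assumed SD, slopes, correlation and discharge rule, and on there being no deaths.

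These are two of eleven secondary endpoints. The primary endpoint and the Stage 1 responder rule do not use this analysis, so the primary conclusion is unaffected. The change is worth making because it is cheap, not because the trial's main result is at risk.

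**What to change.** In section 4.7, for endpoints 3.3.4 and 3.3.5, replace ANCOVA with a repeated-measures mixed model on all daily values. Include arm, day, arm-by-day, baseline, baseline-by-day and a stated within-patient correlation structure. Name one contrast before any data review, either Day 14 or an average over a stated window. Keep Day 14 ANCOVA as a sensitivity analysis. State separately how death is handled, since treating values after death as missing at random is not plausible.

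The cost is wording in section 4.7 (with detail in the analysis plan) and some programming; no new data are needed. The downside is reliance on a covariance form and on discharge being missing at random given the observed readings.
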